7.5 Rejection Criteria

The following criteria should be evaluated in each visit. Possibility of the subject being analyzed as the per protocol set (PPS) population will be compromised without study withdrawal if any of the following occurs:

- 1) Failing to meet the inclusion criteria;
- 2) Meeting the exclusion criteria;
- 3) No data or information collected in follow-ups after vaccination;
- 4) Excessive information and data missing after randomization;
- 5) Subjects who have not been vaccinated, received wrong immunization, or received an incorrect dose.

8 METHODS AND PROCEDURES

8.1 Selection of Subjects

The recruitment for the clinical trial will be performed at the study site approximately two weeks prior to visit 1 (V1). The number of subjects to be enrolled is about 1.5 times of the sample size (may be adjusted according to the actual situation). Investigators with relevant experience will perform such recruitment.

8.2 Informed Consent

The investigator should comply with relevant regulations, GCP, and the ethical principles specified in the "Declaration of Helsinki" during obtaining and recording the informed consent. Before the start of the study, the investigator should obtain the written approval/consent from the Ethics Committee on the informed consent form and other documents provided to the subjects.

Prior to participation in this clinical trial, the investigator should explain the informed consent form to the volunteers and their witnesses and provide sufficient time for them to inquire about the details of the trial before signing the informed consent form. While explaining to multiple persons, the investigator should allow each volunteer and/or witness to ask questions individually before they sign the informed consent form.

The investigator must retain the informed consent form signed by each volunteer for inspection by the pharmaceutical administration department or regulatory personnel. Each subject should be given a copy of the signed and dated informed consent form.

Informed consent must be obtained from each subject.

8.3 On-Site Registration

After the informed consent is obtained from and the informed consent form signed by a volunteer, the investigator will assign a screening number to the volunteer at the registry according to the arrival sequence. The screening number consists of S + site number + 4-digit serial number, starting from SXX0001 for each site.

8.4 Physical Examination and Screening

Subjects are required to undergo a general physical examination, including height/body weight/body temperature and blood pressure. Females of child-bearing age (before menopause) are required to undergo a urine pregnancy test. Subjects in the immunogenicity group are required to undergo immunogenicity, serum IgA, and salivary SIgA tests. Subjects 0001–0060 from a single site managed by the Jiangsu CDC will be included in the cellular immunity group and undergo cytokine testing.

The interviewing physician should conduct medical history inquiry and screening in accordance with the "Inclusion and Exclusion Criteria". Only subjects qualified by screening can be enrolled and randomized.

8.5 Subject Randomization

The investigator will assign each subject in the immunogenicity group a unique randomization number via the IWRS system according to the arrival sequence, without skipping or saving numbers.

8.6 Vaccine and Use

The subject information should be verified before vaccination. Only those who meet the protocol requirements can be vaccinated. Emergency medication and equipment such as epinephrine hydrochloride, simple ventilator, and ECG monitor should be available on-site.

8.6.1 Investigational vaccine

Ad5-nCoV-IH was jointly developed by the Beijing Institute of Biotechnology and CanSino Biologics Inc. The ICV vaccine was developed by Sinovac Biotech Ltd., Beijing Institute of Biological Products Co., Ltd., Wuhan Institute of Biological Products Co., Ltd., and Shenzhen Kangtai Biological Products Co., Ltd.

8.6.2 Immunization route and immunization procedure

Subjects will receive one dose of the investigational vaccine by intramuscular injection or nebulized inhalation at V1 according to the single-dose immunization procedure. The vaccine should be shaken well before use and used immediately after opening. The vaccine should not be used if it expires or has cracks, illegible label, or abnormal physical appearance. Subjects in the intramuscular injection group will receive the vaccine via intramuscular injection at the attachment site of lateral deltoid of the upper arm. The maximum volume of the syringe used for vaccination is recommended to be 1 mL, with a minimum scale of 0.01 mL. Subjects in the nebulized inhalation group will use a nebulizer for oral inhalation.

Nebulized inhalation procedures:

A special device for nebulized inhalation immunization is used.

- (1) Connect the device to the nebulizer cup and ensure that the cup is upright.
- (2) Withdraw corresponding volume of the vaccine with a syringe and inject the investigational vaccine into the area where the nebulization occurs.
- (3) Start the nebulizer and atomize all the vaccine into the nebulizer cup. Remove the nebulizer after nebulization is completed.
- (4) After taking a deep breath, the subject holds the mouthpiece of the nebulizer cup in the mouth, breathes slowly until there is no more mist, and then hold the breath for 5 seconds to complete the immunization.

Precautions:

- (1) The investigational vaccine should be added to the bottom of the cup, without being splashed onto the walls of the cup. The needle should not come into contact with the bottom of the cup.
- (2) The subject do not need to clean the mouth before vaccination but need to fast for food and water for half an hour after completing vaccination.
- (3) The vaccination device can be reused, but the nebulizer cup can only be used once. The vaccination device should be handed over to designated personnel after the end of immunization on the same day.
- (4) Nebulizer cups should be kept upright during atomization and horizontal during inhalation. Handle the nebulizer cups gently and do not shake or press them.
- (5) The subject inhales this product through deep breathing, and after the inhalation is completed, it is required to hold the breath for 5 seconds before exhaling.
- (6) One nebulizer cup can only atomize 0.1 mL.

8.6.3 Storage and transportation of investigational vaccines

- 1) Vaccine packaging: As this is an open-label study, blinded packaging is not required.
- 2) Vaccine storage: The investigational vaccines shall be stored in a safe and locked place, and shall not be accessed by any person unauthorized. The vaccines should be stored at 2–8 °C. The storage temperature should be recorded once every morning and afternoon on each working day.
- 3) Vaccine transportation: CanSino Biologics Inc. is responsible for transporting the Ad5- nCoV-IH vaccine from the manufacturing site to the clinical trial sites under refrigeration and submitting the investigational vaccines to the study sites along with the shipping temperature records (meeting the cold chain temperature for the vaccine) and the certificate of analysis (qualified), which should be checked, signed, and received by the vaccine manager of each clinical trial site. Each study site will provide ICV vaccines.

Each freezer, refrigerator, and cold chain equipment should be equipped with thermometers for investigational vaccine storage on the vaccination site and during transportation from the study site to the vaccination site and vice versa. The vaccine manager shall record the temperature every 30 min, including detailed transportation and storage temperature records. The vaccines must be transported within the storage temperature (2–8 °C). Any temperature deviations must be reported to the study center for further instructions. All vaccine shipments must be documented.

8.6.4 Concomitant medication

If a subject experiences a medical event during the study, appropriate treatment and medical treatment will be allowed, but the medication or medical treatment should be recorded in a timely manner. Any types of vaccines administered to the subjects during the study are required to be recorded in detail.

The concomitant medications of subjects within 28 days after each vaccination should be recorded in the diary card, and the concomitant medications for SAEs throughout the entire observation period should be entered in the EDC system.

Subjects are not recommended to receive other vaccines during the study, except for emergent vaccination due to emergencies involving rabies vaccine, tetanus vaccine, and other vaccines required. The concomitant vaccines used within 28 days after vaccination should be recorded in the diary card.

8.6.5 Organization and management of investigational vaccines

The investigator is responsible for the vaccination, recovery, and inventory checking of the investigational vaccines, as well as accurate and timely recording and archiving. At the end of the study, the investigator should return all remaining investigational vaccines and their packaging materials to the study center. The investigator may not use the investigational vaccine under any circumstance or on any occasion not specified in this protocol.

8.7 Safety Follow-Up and Evaluation

8.7.1 Safety observation

All subjects will remain on site for a 30-min observation period after receiving the vaccination. Investigators will observe each and every one of the subjects and record both regional and systemic responses reported during the 30-min observation period, as well as their severity.

A safety follow-up will be performed within 14 days after vaccination for all subjects, during which the investigator will systematically examine each subject for ARs, and the subject will fill in the "Vaccination Diary Card (Within 14 Days)" according to their symptoms and signs. From day 15 to day 28 after vaccination, post-vaccination AEs should be observed through spontaneous reporting and regular follow-ups. The investigators will inquire and check the diary cards at the next visit and guide the subjects in completing the cards. From day 28 to month 6 after vaccination, safety follow-ups on SAEs should be performed by spontaneous reporting.

8.7.2 Contents and parameters of safety observation

Based on the types and incidence of ARs observed in previous clinical trials as well as the ARs listed in the package inserts of similar products available on the market, this study has adhered to the "Guidelines for Grading Criteria of Adverse Reactions in Clinical Trials of Preventive Vaccines" (No. [2019]102 issued by NMPA). The contents and parameter grades of post-vaccination safety observations are presented in Tables 8.7-1 to 8.7-3, and the grading of vital sign-related safety is shown Table 8.7-4.

Table 8.7-1. Grading of administration-site (local) AEs of the nebulized inhalation vaccine

Symptoms/Signs	Grade 1	Grade 2	Grade 3	Grade 4
Dry mouth	Transient, not requiring treatment, and not affecting daily activities	Dry mouth, slightly affecting daily activities	Seriously affecting daily activities and requiring treatment	NA
Hoarseness	Transient, not requiring treatment, and not affecting daily activities	Hoarseness, affecting normal speech	Seriously affecting daily activities and requiring treatment	NA
Mucositis oral	Transient, not requiring treatment, and not affecting daily activities	Slightly affecting daily activities	Seriously affecting daily activities and requiring treatment	NA
Throat swelling	Transient, not requiring treatment, and not affecting daily activities	Throat redness and swelling, slightly affecting swallowing function	Seriously affecting daily activities and requiring treatment	NA
Pharyngalgia	Transient, not requiring treatment, and not affecting daily activities	Pain pharynx, slightly affecting daily activities	Severe pharyngalgia, seriously affecting daily activities, and requiring drug treatment	NA

Table 8.7-2. Grading of injection-site (local) AEs of the intramuscular vaccine

Symptoms/Signs	Grade 1	Grade 2	Grade 3	Grade 4
Pain	Not affecting or slightly affecting limb activities	Affecting limb activities	Affecting daily activities	Leading to loss of basic self-care ability or hospitalization
Induration*, swelling** #	Diameter of 2.5 cm to < 5 cm or area of 6.25 cm ² to < 25 cm ² and not or slightly affecting daily life	Diameter of 5 cm to < 10 cm or area of 25 cm ² to < 100 cm ² or affecting daily life	Diameter ≥ 10 cm, or area ≥ 100 cm ² , or ulceration, secondary infection, phlebitis, aseptic abscess, or wound drainage, or seriously affecting daily activities	Abscess, exfoliative dermatitis, or necrosis of dermal or deep tissues
Rash* and redness** #	Diameter of 2.5 cm to < 5 cm or area of 6.25 cm ² to < 25 cm ² and not or slightly affecting daily life	Diameter of 5 cm to < 10 cm or area of 25 cm ² to < 100 cm ² or affecting daily life	Diameter ≥ 10 cm, or area ≥ 100 cm ² , or ulceration, secondary infection, phlebitis, aseptic abscess, or wound drainage, or seriously affecting daily activities	Abscess, exfoliative dermatitis, or necrosis of dermal or deep tissues
Pruritus	Pruritus at the injection site, relieved spontaneously or within 48 h after treatment	Pruritus at the injection site, not relieved within 48 h after treatment	Affecting daily activities	NA
Cellulitis	NA	Requiring non-injection treatment (e.g., oral antibacterial, antifungal, and antiviral treatment)	Requiring intravenous injection treatment (e.g., intravenous antibacterial, antifungal, and antiviral treatment)	Sepsis or tissue necrosis, etc.

Notes: * In addition to grading and evaluation by direct measurement of diameter, progress and changes in the measurement results should also be recorded.

** The greatest measured diameter or area should be used.

For the evaluation and grading of induration and swelling, rash, and redness, indicators with greater grades should be selected based on the functional grades and actual measurement results.

Table 8.7-3. Grading of non-injection-site (systemic) AEs (sore throat is a systemic AE in the case of intramuscular injection)

Symptoms/Signs of organs/systems	Grade 1	Grade 2	Grade 3	Grade 4
Diarrhea	Mild or transient, 3–4 times/day, abnormal stool properties, or mild diarrhea for less than 1 week	Moderate or persistent, 5–7 times/day, abnormal stool properties, or diarrhea > 1 week	> 7 times/day, abnormal stool properties, or hemorrhagic diarrhea, orthostatic hypotension, electrolyte imbalance, and requiring intravenous infusion > 2 L	Hypotensive shock, requiring hospitalization
Nausea	Transient (< 24 h) or intermittent, normal food intake	Persistent nausea resulting in decreased food intake (24–48 h)	Persistent nausea resulting in minimal food intake (> 48 h) or rehydration indicated (e.g., IV fluids)	Life-threatening consequences (e.g., hypotensive shock)
Anorexia	Decreased appetite, without reduced food intake	Decreased appetite associated with decreased food intake, without significant weight loss	Decreased appetite, associated with significant weight loss	Intervention indicated (e.g., gastric tube feeding and parenteral nutrition)
Vomiting	1–2 episodes/24 h and no interference with activity	3–5 episodes/24 h or some interference with activity	Over 6 episodes within 24 h or requiring intravenous fluids	Requiring hospitalization or other nutritional supplement ways for hypotensive shock
Fatigue and asthenia	Not affecting daily activities	Affecting normal daily activities	Seriously affecting daily activities, unable to work	Requiring emergency treatment or hospitalization
Headache	Not affecting daily activities, not requiring treatment	Transient, slightly affecting daily activities, possibly requiring treatment or intervention	Seriously affecting daily activities, requiring treatment or intervention	Refractory, requiring emergency treatment or hospitalization
Arthralgia	Mild pain, not interfering with functions	Moderate pain, requiring analgesics and/ or pain hinders the function, but not affecting daily activities	Severe pain, requiring analgesics and/ or pain affecting daily activities	Disabling pain

Symptoms/Signs of organs/systems	Grade 1	Grade 2	Grade 3	Grade 4
Chest pain	Mild pain, not interfering with functions	Moderate pain, requiring analgesics and/or pain hinders the function, but not affecting daily activities	Severe pain, requiring analgesics and/or pain affecting daily activities	Disabling pain
Pharyngalgia	Transient, not requiring treatment, and not affecting daily activities	Pain pharynx, slightly affecting daily activities	Severe pharyngalgia, seriously affecting daily activities, and requiring drug treatment	NA
Rhinorrhea	Transient, not requiring treatment	Persistent, treatment effective	Treatment uncontrollable	Requiring emergency treatment or hospitalization
Sneezing	Transient, not requiring treatment	Persistent, treatment effective	Treatment uncontrollable	Requiring emergency treatment or hospitalization
Cough	Transient, not requiring treatment	Persistent cough, treatment effective	Paroxysmal cough, treatment uncontrollable	Requiring emergency treatment or hospitalization
Muscle pain at non-injection sites	Not affecting daily activities	Slightly affecting daily activities	Severe muscle pain, seriously affecting daily activities	Requiring emergency treatment or hospitalization
Pruritus at non-injection sites (no skin damage)	Slight itching, not affecting or slightly affecting daily activities	Pruritus affecting daily activities	Pruritus, causing inability to perform daily activities	NA
Skin and mucosal abnormalities	Erythema/pruritus/color changes	Diffuse skin rash/rash maculopapular/dryness/desquamation	Blister/exudation/desquamation/ulceration	Dermatitis exfoliative involving mucosa, erythema multiforme, or suspected Stevens-Johnsons syndrome
Acute anaphylactic reactions**	Local urticaria (blister), not requiring treatment	Local urticaria requiring treatment, or mild angioedema not requiring treatment	Extensive urticaria or angioedema requiring treatment, or mild bronchospasm	Anaphylactic shock, or life-threatening bronchospasm, or laryngeal edema

Symptoms/Signs of organs/systems	Grade 1	Grade 2	Grade 3	Grade 4
Syncope	Near syncope, without loss of consciousness (e.g., presyncope)	Loss of consciousness, not requiring treatment	Loss of consciousness, requiring treatment or hospitalization	NA
Constipation*	Requiring stool softeners and diet adjustment	Requiring laxatives	Obstipation, requiring manual bowel movement or enema	Toxic megacolon or bowel obstruction
Dysphagia	Mild discomfort when swallowing	Restricted diet	Great limitations in eating and talking; unable to consume solid food	Unable to consume liquid food; requiring intravenous nutrition
Arthritis	Mild pain, with inflammation, erythema, or joint swelling; but not interfering with functions	Moderate pain, with inflammation, erythema, or swelling of the joints; interfering with functions, but not affecting daily activities	Severe pain, with inflammation, erythema, or swelling of the joints; affecting daily activities	Permanent and/or disabling joint injuries
New-onset convulsion	NA	NA	1–3 convulsion(s)	Prolonged and multiple convulsions (e.g., status epilepticus) or uncontrollable convulsions (e.g., refractory epilepsy)
Acute bronchospasm	Transient, not requiring treatment; FEV ₁ %: 70%–80%	Requiring treatment: return to normal after treatment with bronchodilators; FEV ₁ %: 50%–70%	Unable to return to normal after treatment with bronchodilators; FEV ₁ %: 25%–50%, or persistent intercostal retraction	Cyanosis, FEV ₁ %: < 25%, or requiring intubation
Dyspnea	Dyspnea during exercise	Dyspnea during normal activities	Dyspnea at rest	Dyspnea, requiring oxygen therapy, hospitalization, or assisted breathing
Insomnia*	Slight sleep problem, not affecting or slightly affecting daily activities	Moderate sleep problem, affecting daily activities	Severe sleep problem, seriously affecting daily activities and requiring treatment or hospitalization	NA
Irritation or suppression	Mild irritation or mild suppression	Irritability or lethargy	Inability to be soothed or poor response	NA

Symptoms/Signs of organs/systems	Grade 1	Grade 2	Grade 3	Grade 4
Mental disorders (including anxiety, depression, mania, and confusion), for which the detailed symptoms should be reported	Mild symptoms, not requiring medical consultation, or the act not affecting or slightly affecting daily activities	Presence of clinical symptoms, requiring medical consultation, or the act affecting daily activities	Requiring hospitalization, or behavioral ability not supporting the daily life	Tending to harm oneself or other people, or acute mental confusion, or loss of ability for basic self-care
Pain at non-injection sites# (sites should be identified when reporting)	Slight pain, not affecting or slightly affecting daily activities	Pain, affecting daily activities	Pain, causing inability to perform daily activities	Disabling pain, leading to loss of basic self-care ability
Fever※ [axillary temperature (°C)]	37.3 to < 38.0	38.0 to < 38.5	38.5 to < 39.5	≥ 39.5, lasting ≥ 3 days

Notes: FEV₁% = Forced expiratory volume in one second (FEV₁)/Forced vital capacity (FVC)

* Changes in constipation and insomnia before and after vaccination should be noted.

** Type I hypersensitivity.

Pain at non-injection sites other than muscle pain, arthralgia, and headache.

※ Generally, the axillary temperature is used in China and converted to the oral temperature and rectal temperature as necessary. Generally, oral temperature = Axillary temperature + 0.2 °C; rectal temperature = axillary temperature + (0.3–0.5 °C). In the case of persistent hyperpyrexia, its cause should be identified where possible.

Local AEs are all solicited events. Among the above non-injection site (systemic) AEs, solicited AEs include sore throat (considered a systemic AE in the case of intramuscular injection), fever, diarrhea, fatigue, asthenia, nausea, anorexia, vomiting, headache, cough, arthralgia, chest pain, muscle pain at non-injection sites, pruritus at non-injection sites (without skin damage), skin and mucosal abnormalities, rhinorrhea, and sneezing, while the rest are unsolicited AEs. Refer to the Investigator's Brochure for other non-solicited AEs.

General rules for grading of other AEs:

For clinical abnormalities not described in the grading tables above, the severity grading and assessment for AEs are conducted according to the following criteria:

Grade 1	Grade 2	Grade 3	Grade 4	Grade 5
Mild: short-term (< 48 h) or mild discomfort, not affecting activities and not requiring treatment	Moderate: mild or moderate restricted activities, potentially requiring medical consultation, and not requiring treatment or only requiring mild treatment	Severe: obviously restricted activities, requiring medical consultation and treatment, and potentially requiring hospitalization	Critical: potentially life-threatening, severely restricted activities, and requiring monitoring and treatment	Death

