3.4.2 A Heterologous clinical study on nebulized inhalation

In August 2021, a single-center, randomized, open-label, parallel-controlled clinical study was carried out in Donghai County, Jiangsu to evaluate the safety and immunogenicity of different doses of recombinant COVID-19 vaccine (adenovirus type 5 vector) for inhalation in people aged 18 years and above.

A total of 420 subjects aged 18 years and above were required to be enrolled in this study. Eligible subjects who provided informed consent and passed screening were randomly assigned at a ratio of 1:1:1 to Heterologous low-dose booster immunization group (group A), Heterologous high-dose immunization group (group B), and routine booster immunization group (group C). Subjects in groups A, B, and C must have completed prime immunization with 2 doses of the inactivated SARS-CoV-2 vaccine. Subjects enrolled in the study received a booster dose with either the inactivated SARS-CoV-2 vaccine or recombinant COVID-19 vaccine (adenovirus type 5 vector) for inhalation at 3–9 months after the aforementioned 2-dose vaccinations. The first 40 subjects in each group were included in the immunogenicity subgroup for immunogenicity monitoring.

Preliminary results:

Booster immunization showed good safety in all groups, and most ARs were of grade 1. The main local ARs in the nebulized inhalation group included dysphonia, dry mouth, oral mucositis, and pharyngeal swelling, while those in the intramuscular injection group (group C) included pain, swelling, and pruritus. The incidences of local ARs in the nebulized inhalation groups were lower than those in the intramuscular injection groups. Main systemic ARs reported by all groups were pyrexia, fatigue, and headache, and inter-group differences were not statistically significant.

Fourteen days after booster immunization, the incidences of overall solicited ARs in groups A, B, and C were 26 (18.57%), 33 (23.57%), and 54 (38.57%), respectively, with inter-group differences statistically significant ($P = 0.0004$); the incidences of grade 3 ARs were 2 (1.43%), 2 (1.43%), and 0 (0.00), with $P = 0.5524$.

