8.11.4.2.2 Incidence of adverse reactions within 0–14 days post-vaccination

The number of subjects, number of events, and percentage of adverse reactions occurring within 0–14 days post-vaccination in each group will be summarized. The number of subjects, number of events, and percentage of adverse reactions occurring within 0–14 days post-vaccination in each group will be summarized by severity and symptom. The inter-group comparison is performed using chi-square test or Fisher's exact test.

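### Dry mouth, hoarseness, oral mucositis and throat swelling are solicited after the inhaled vaccine but not after ICV, so between-group comparisons of these four symptoms rest on unequal ascertainment

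*Protocol*

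**What the plan says.** Section 8.7.2 gives each route its own local list. "Table 8.7-1. Grading of administration-site (local) AEs of the nebulized inhalation vaccine" covers dry mouth, hoarseness, oral mucositis, throat swelling and pharyngalgia. "Table 8.7-2. Grading of injection-site (local) AEs of the intramuscular vaccine" covers pain, induration and swelling, rash and redness, pruritus and cellulitis, with no mouth or throat item.

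The text after Table 8.7-3 sets solicitation status: "Local AEs are all solicited events. Among the above non-injection site (systemic) AEs, solicited AEs include sore throat (considered a systemic AE in the case". The parenthesis refers to the injected route. The systemic list then runs through general symptoms such as fever, headache and cough, and it ends with the words "while the rest are unsolicited AEs".

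The analysis text then compares the groups. For days 0–14 (section 8.11.4.2.2), the number of subjects, number of events and percentage of adverse reactions "in each group will be summarized by severity and symptom. The inter-group comparison is performed using chi-square test or Fisher's exact test". Sections 8.11.4.2.1 (30 minutes) and 8.11.4.2.3 (days 0–28) are worded alike. None of them limits the comparison to symptoms solicited in both groups.

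**The concern.** A symptom that is asked about is recorded more completely than one that is not. Injection-site pain cannot occur after inhalation, so soliciting it only after an injection does no harm to a comparison of that symptom. Dry mouth or hoarseness can occur in anyone. The protocol accepts this reasoning for sore throat, which it solicits in both arms, but not for the other four symptoms in the same table.

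The four are not marginal. Section 3.4.2, on the earlier heterologous booster study, reports: "The main local ARs in the nebulized inhalation group included dysphonia, dry mouth, oral mucositis, and pharyngeal swelling". The safety group of about 10,000 has no control, so the randomized ICV arm is the only concurrent source for the background rate of these symptoms. If they are under-recorded there, the trial cannot say how much of the inhaled vaccine's local profile is due to the vaccine. No later analysis can recover what was not asked. It can only drop the comparison.

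**Working it through.** No sample size, power or error rate in the protocol depends on this point, so there is no stated figure to reproduce. The check has a textual part and an illustration of size.

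**1. Solicitation status by arm (section 8.7.2)**

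| Symptom | After Ad5-nCoV-IH | After ICV |
|---|---|---|
| Sore throat / pharyngalgia | Solicited, local | Solicited, systemic |
| Dry mouth | Solicited, local | Unsolicited |
| Hoarseness | Solicited, local | Unsolicited |
| Oral mucositis | Solicited, local | Unsolicited (partial overlap with the solicited item on skin and mucosal abnormalities) |
| Throat swelling | Solicited, local | Unsolicited |
| Injection-site items | Not applicable | Solicited, local |

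**2. Inputs for the illustration**

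- From the protocol: 420 subjects randomized 1:1, so n = 210 per arm (section 6); two-sided α = 0.05 (section 8.11.4); chi-square or Fisher's exact test (section 8.11.4.2).
- Assumed, because the protocol gives neither: the true rate p of one symptom, equal in both arms, and the fraction c of events captured and counted after ICV relative to the inhaled arm.

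**3. Formula**

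P(false excess) = Σ over a > b of Bin(a; 210, p) × Bin(b; 210, c·p), summed over pairs whose two-sided Fisher p-value is below 0.05. For orientation, 6/210 against 0/210 gives p = 0.030 and 5/210 against 0/210 gives p = 0.061.

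**4. Chance of a false significant excess in the inhaled arm**

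| Captured after ICV (c) | p = 1% | p = 2% | p = 3% | p = 5% |
|---|---|---|---|---|
| 1 (equal) | 0.3% | 0.9% | about 1% | 1.5% |
| 0.5 | 0.7% | 4.9% | 9.5% | 18.9% |
| 0.25 | 1.2% | 11.1% | 25.2% | 50.3% |

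At p = 1% the figure reaches only 2.0% even if nothing is captured after ICV. If chi-square is used wherever expected counts are at least 5, the p = 5% figures rise to 26.7% (c = 0.5) and 60.9% (c = 0.25).

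**5. How plausible are these background rates?**

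In the earlier booster study (section 3.4.2), any solicited local reaction, all symptoms together and vaccine-caused ones included, occurred in 9/140 = 6.43% and 16/140 = 11.43% of the two inhaled arms. A 5% background for a single symptom would be close to the whole of the lower total, so 5% is at the high end.

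**6. The overall reaction rate**

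From the same study, subjects with local reactions only = overall minus systemic:

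- inhaled low dose: 26 − 26 = 0
- inhaled high dose: 33 − 27 = 6, and 6/140 = 4.3 points
- ICV: 54 − 21 = 33, and 33/140 = 23.6 points

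Local items solicited only after ICV therefore weigh more in the overall rate than those solicited only after inhalation.

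**The case against.** Several points on the other side stand.

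- Section 8.7.1 gives every subject a 14-day diary card and a systematic examination by the investigator, and the visit table requires all adverse events to day 28 to be documented. A reader might infer that the four symptoms are recorded after ICV only if volunteered. The documents do not support that. Capture is reduced, not absent. The diary card is not shown, so what ICV recipients are asked is partly inferred from the solicited list.
- A reader might infer that the whole adverse-reaction comparison is biased against the inhaled vaccine. It is not shown to be: injection-site items are solicited only after ICV and push the overall rate the other way.
- A reader might cite the phase II placebo rate in section 3.4.1, (13 + 5)/120 = 15%, as an inhaled-placebo background. Those placebo subjects are pooled across groups that include intramuscular and mixed-route schedules, and the section reports few local reactions. The figure says nothing about oropharyngeal background.
- The tests concern adverse reactions, so attribution also matters. The rule that solicited local events are related by definition (section 8.7.4) speaks of injection sites. Whether it covers inhalation-local events is a matter of reading.
- It is not clear which grading applies to these symptoms after ICV. The general rule is for abnormalities not described in the tables, and Table 8.7-1 does describe them, but for the nebulized vaccine.
- Testing symptom by symptom is the natural reading of section 8.11.4.2 but is not spelled out, and the only formal hypothesis is on immunogenicity.

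Route-specific solicitation of local events may well be deliberate. That does not answer the point, because the protocol already departs from it for sore throat.

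**Conclusion.** The concern holds for the four symptoms and no further. Section 8.7.2 makes them solicited in one randomized arm and unsolicited in the other, and any between-group comparison of them under sections 8.11.4.2.1 to 8.11.4.2.3 tends to show an excess after inhalation. The size is uncertain: negligible at 1% background, and between about 5% and 50% chance of a false finding per symptom over backgrounds of 2% to 5% with a quarter to a half of events captured after ICV. This assumes 210 per arm, equal true rates, a Fisher test, and captured events being counted as reactions. The primary immunogenicity comparison is untouched. The point is worth correcting because the loss arises at data collection and the remedy is small.

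**What to change.** In section 8.7.2, make dry mouth, hoarseness, oral mucositis and throat swelling solicited for every subject in the randomized immunogenicity group, whichever vaccine is given. Record them on the same 0–14 day diary card and grade them with Table 8.7-1, extending what is already done for sore throat.

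If the cards are already in use, state in section 8.11.4.2 that between-group symptom tests are limited to terms solicited in both arms. Report route-specific local terms, injection-site items included, descriptively by arm.

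The cost is four extra rows on the card for about 210 ICV recipients and a sentence in section 8.7.2. The downside is a slightly longer card and a slightly higher recorded event and reaction count in the ICV arm.
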